#### **STUDY DESIGN:**

This will be a single center prospective study to assess the role of EUS and ultrasound elastography in patients with ARP and CP. This pilot study will catalogue EUS and elastography findings in children with ARP and CP and compare with healthy controls.

Additionally, we plan to evaluate sonographic markers for pancreas fibrosis in children, including EUS elastography which we will compare to transabdominal ultrasound elastography for assessment of pancreatic parenchymal stiffness. Elastography and grayscale EUS findings will be benchmarked against parenchymal histology for patients undergoing pancreatic surgery (e.g. total pancreatectomy with islet Autotransplantation).

Data derived from this study including EUS findings in pediatric patients with ARP and CP, and US markers of pancreatic fibrosis, will serve as the foundation for more extensive studies of pediatric pancreatitis with EUS. Additionally, this may serve as preliminary data for establishment of pediatric EUS criteria for CP and early CP.

### **STUDY PROCEDURES:**

Approximately 60 participants will be recruited to enroll in the study. Forty participants will have ARP or CP as defined by the International Study Group of Pediatric Pancreatitis: In search for a cure (INSPIRE)[18]. Twenty participants from this cohort will be undergoing TPIAT or other pancreatic resection. Another twenty participants will be controls with no history of pancreatic disease undergoing EUS for other clinical indications.

#### *Procedures and Imaging:*

EUS will be performed as part of routine clinical care using a GF-UCT180 curvilinear array ultrasound gastroscope (Olympus America Inc; Center Valley, PA). Grayscale findings (Table 1) will be recorded and documented for clinical care. Research EUS SWE measurements will be obtained using the Aloka Arietta 850 AT processor (Olympus America Inc; Center Valley, PA) with SWE measurements taken from each of the head, genu, body and tail of the pancreas. Research TUS SWE will be performed using a Canon Aplio i800 ultrasound system and a curved 1-6 MHz transducer. 2D SWE will be performed with measurement of shear wave speed in the head, body and tail of the pancreas.

Modality	Findings
EUS	Rosemont and Conventional Criteria
MRI	Atrophy T1 signal (signal intensity ratio, relaxometry) Enhancement Cambridge Criteria
CT	Atrophy Calcifications Duct dilation
ERCP	Cambridge Criteria

**Table 1:** EUS and other imaging findings to be catalogued and compared for diagnosis of CP

MRCP or CT imaging within 3 months of the EUS will be reviewed blinded to EUS and SWE findings for findings of CP (Table 1). Fluoroscopic pancreatogram images from patients with an ERCP within this time frame will be scored using Cambridge Criteria.[19]

Research EUS SWE measurements are anticipated to add approximately 5 minutes to the total procedure time. Research TUS SWE will take no more than 20 minutes and may or may not occur on the same day as the EUS procedure.

**Specimen histology:** A small core of pancreatic tissue is routinely collected from all patients undergoing TPIAT at our institution and a similar sample would be obtained from patients undergoing other resections. Findings from enrolled participants' samples will be reviewed for the presence of fibrosis using a four-stage scoring system adopted by Wellner et al.

Data collected from Epic may include: patient age, sex, height/ weight, relevant lab values, results of imaging modalities (MRCP, CT, US, or ERCP, EUS), relevant genetic testing results, pancreatic function testing results, medications, hospital stay, complications, clinical course, interventions/surgical procedures, and other relevant clinical data.

**STUDY POPULATION:**

There will be two cohorts for the study.

**Pancreatitis Cohort:**

*Inclusion criteria:*

- Confirmed diagnosis of ARP or CP by INSPIRE criteria
- ≤ 21 years of age, male and female
- Children undergoing EUS for clinical care
- For Aim 2.3 only: Children undergoing TPIAT or other pancreatic resection

*Exclusion criteria:*

- Children <15 kg who cannot accommodate the size of endoscope
- Children with acute pancreatitis (AP) <6 weeks prior to EUS

**Control Cohort:**

*Inclusion criteria:*

- Children without a history of pancreatic disease undergoing EUS for other clinical indications
- ≤ 21 years of age, male and female

*Exclusion criteria:*

- Children <15 kg who cannot accommodate the size of endoscope
- Children with AP, ARP or CP

**Definitions:**

Acute pancreatitis (AP): The presence of at least 2 out of 3 criteria: 1) abdominal pain (acute onset, epigastric, possibly radiating to the back); 2) serum amylase and/or lipase of at least 3 times greater than the upper limit of normal; and 3) characteristic findings of acute pancreatitis on imaging such as ultrasound, computed tomography, magnetic resonance imaging (i.e. pancreatic edema, areas of pancreatic or peripancreatic necrosis, peripancreatic inflammation).[18]

Acute Recurrent Pancreatitis (ARP): The presence of at least 2 distinct episodes of AP as defined above, along with 1) complete resolution of pain and a >1 month pain-free interval between diagnoses of AP; or 2) complete normalization of serum amylase and lipase before the subsequent episode of AP is diagnosed, along with complete resolution of pain, irrespective of a specific time interval.[18]

Chronic Pancreatitis (CP): The presence of at least one **irreversible structural change\*** in the pancreas with or without abdominal pain +/- exocrine pancreatic insufficiency +/- diabetes.[18]

***\*irreversible structural changes:***

- *Ductal calculi, dilated side branches, parenchymal calcifications found in any imaging (abdominal ultrasound (abd US), magnetic resonance imaging/magnetic resonance cholangiopancreatography (MRI/MRCP), computerized tomography (CT), endoscopic retrograde cholangiopancreatography (ERCP), endoscopic US (EUS).*

- *Ductal obstruction or stricture/dilatation/irregularities that are persistent (for >2 months) on any imaging.*
- *Parenchymal atrophy, irregular contour, accentuated lobular architecture, cavities alone are not diagnostic findings for CP.*
- *Surgical or pancreatic biopsy specimen demonstrating histopathologic features compatible with CP (acinar atrophy, fibrosis, protein plugs, infiltration with lymphocytes, plasma cells, macrophages).*

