## **RECRUITMENT AND CONSENT:**

### *Subject Recruitment:*

Recruited subjects will be identified through review of patients presenting for EUS for clinical care. Potential participants for the pancreatitis cohort will be reviewed to confirm diagnosis of ARP or CP by INSPIRE criteria. We are requesting a waiver of consent for chart review to confirm eligibility of the subjects for the study.

Potential participants for the control cohort will be identified by the primary investigator at the time of scheduling. These control patients will be undergoing EUS for other clinical indication. Following screening, patients will be enrolled by the research staff after informed consent is obtained through the informed consent process mentioned below. We plan to approach for enrollment, all pediatric patients that meet inclusion criteria during the funding period and anticipate no difficulty achieving our recruitment targets based on the robust referral base for our pediatric Pancreas Care Center.

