### *Process of obtaining Consent (including eConsent):*

Consent, parental permission and/or assent will be obtained from all patients (pancreatitis cohort and control cohort) before any study-related procedures are performed. Written assent will be obtained from participants 11 years of age and older. The investigator will be available to answer any questions that the participant or parent may have regarding procedures, risks, and alternatives. The consent process will be documented on the informed consent progress note.

Consent may take place by several methods: in-person paper consent, in-person electronic consent (using REDCap for the eConsent) or over the phone (via paper or REDCap for eConsent). Signatures of the subject and study staff may not always occur on the same date depending on how and when the subject returns the signed consent. No matter the consenting process, study procedures will not occur prior to a fully executed consent form. Consent will be obtained following the CCHMC consenting SOP. REDCap eConsent will not replace the consenting method, it will be used as an additional resource for signing the consent form. A copy of the consent form will either be given to the subject in paper form or emailed to them via REDCap depending on how the consent is completed. In all cases, the consent process will be documented on the informed consent process note and a copy of the signed consent(s) will be kept in the patient's medical record.

Staff will make sure that the eConsent database is updated as soon as possible after a new version of the paper consent is approved. Staff will also make sure paper consents are used to consent eligible subjects in the event that the eConsent database is not updated prior to eligible subjects being available for consent approach by a member of the study staff. For the reasons described, the eConsent will not be submitted to the IRB for approval.

Subjects will be reminded that participation in research is completely voluntary. Coercion is eliminated by having the subjects sign an assent document and the parent/guardian signs the consent document. We will give potential subjects time to read the consent form, consent them in a private setting, and answer any questions they may have.

Potential subjects (or parents) will be told that the subject's (parent's) decision to participate will not affect the clinical care received.

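### Aim 1.2 hypothesises that grayscale EUS is more sensitive, but only association tests are planned; the promised grayscale EUS versus histology analysis is missing; EUS findings may also help define CP

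*Combined protocol and SAP*

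**What the plan says.** **Hypothesis and planned tests.** Specific Aims, Aim 1.2, hypothesises that grayscale EUS is the more sensitive modality at every stage of CP. The comparators are ERCP, MRCP and CT done for clinical reasons within 3 months either side of the EUS. Under Statistical analysis, Aim 1 has frequencies of EUS findings in ARP, CP and controls, with Fisher's exact and chi-square tests between groups. The same tests are to be used for the relationship between EUS and other imaging. Sensitivity and specificity appear only under Aim 2, and only for shear wave elastography (SWE).

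**Histology.** The Study Design section says that both elastography and grayscale EUS will be benchmarked against histology in children having pancreatic surgery. Aim 2.3 and the Aim 2 analysis use histology for SWE alone. Study Procedures places 20 of the 40 pancreatitis participants in the surgical group.

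**The CP label.** Under Definitions, one irreversible structural change establishes CP. Qualifying changes include "Ductal calculi, dilated side branches, parenchymal calcifications found in any imaging", and the listed modalities end with "endoscopic retrograde cholangiopancreatography (ERCP), endoscopic US (EUS". Also qualifying are "Ductal obstruction or stricture/dilatation/irregularities that are persistent (for >2 months) on any imaging" and "Surgical or pancreatic biopsy specimen demonstrating histopathologic features compatible with CP". Cohort entry requires "Confirmed diagnosis of ARP or CP by INSPIRE criteria", checked at screening: "Potential participants for the pancreatitis cohort will be reviewed to confirm diagnosis of ARP or CP by INSPIRE criteria". Under the consent section, "study procedures will not occur prior to a fully executed consent form". Controls exclude "Children with AP, ARP or CP".

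**The concern.** A claim that one test is more sensitive than another needs three things: a reference that says who has the disease, a comparison within the same children, and a measure that has a direction. The Aim 1.2 analysis names none of them. A small p-value would show only that EUS and the other modality tend to be positive in the same children, yet it could be read as support for the hypothesis.

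The tissue reference that does not depend on imaging is histology in the resected children. The protocol promises to use it for grayscale EUS, but no analysis does so.

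The label adds a smaller problem. Where an earlier EUS finding made a child CP rather than ARP, comparing CP with ARP on that same finding is partly circular. The protocol does not ask for the modality that established CP. This matters because the Study Design section says the data may serve as preliminary data for pediatric EUS criteria.

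**Working it through.** The plan gives no sample-size or accuracy figure to reproduce, and it states that no power calculation was done. The ARP/CP split, the number with both tests and all accuracies below are therefore assumptions.

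**1. What the planned test can show.** Assume 24 children with both EUS and one comparator.

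| Both + | EUS only | Comparator only | Neither | Fisher p | Exact McNemar p |
|---|---|---|---|---|---|
| 10 | 8 | 0 | 6 | 0.024 | 0.008 |
| 10 | 0 | 8 | 6 | 0.024 | 0.008 |
| 14 | 2 | 2 | 6 | 0.005 | 1.00 |

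- Row 1: EUS is positive in 18/24 and the comparator in 10/24, a difference of 8/24 = 33 points. Row 2 is the mirror image, -33 points.
- Fisher's p is the same in both. The margins are 18/6 and 10/14. The observed table has probability C(18,10)/C(24,10) = 43,758/1,961,256 = 0.0223. The other tail, with 4 positive on both, adds 0.0016, giving 0.0239.
- Row 3: each modality is positive in 16/24, so there is no difference, yet Fisher's p is 0.005.
- Overall agreement is also blind to direction: it is 16/24 in rows 1 and 2 alike.
- Exact McNemar uses only the discordant children: 2 × 0.5^8 = 0.0078 for 8 against 0, and 1.00 for 2 against 2. Its p-value is two-sided, so the discordant counts must be shown to give the direction.

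**2. What a paired test could deliver.** At two-sided 0.05 it needs at least 6 discordant children, all in one direction (2 × 0.5^6 = 0.031; five give 0.0625). Assume 20 CP children with both tests and independent errors. The power is then 16% for true rates of 80% against 60%, and 44% for 90% against 60%.

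**3. Histology in about 20 children.** Exact (Clopper-Pearson) 95% intervals, if all 20 have fibrosis: 12/20 gives 36-81%, 16/20 gives 56-94%, 18/20 gives 68-99%.

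**4. The label.** Let r be the share of EUS-positive, MRCP-negative children whose EUS result enters the CP label. Assume 25 CP and 15 ARP, both tests 80% sensitive, false positives 20% for EUS and 5% for MRCP, and independent errors.

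- Positive on both: 25 × 0.64 + 15 × 0.2 × 0.05 = 16.15. EUS only: 25 × 0.16 + 15 × 0.2 × 0.95 = 6.85. All MRCP-positive: 25 × 0.8 + 15 × 0.05 = 20.75. Neither: 25 × 0.04 + 15 × 0.8 × 0.95 = 12.4.
- True CP-minus-ARP contrast in EUS positivity: 80 - 20 = 60 points.
- r = 0: 16.15/20.75 - 6.85/19.25 = 42.2 points.
- r = 1: (16.15 + 6.85)/(20.75 + 6.85) - 0/12.4 = 83.3 points.

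Bias in points (reported minus true) at r = 0 and r = 1:

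| False positives EUS/MRCP | 25/15 split | 20/20 split |
|---|---|---|
| 20%/5% | -17.8, +23.3 | -14.0, +23.3 |
| 5%/5% | -22.2, +6.5 | -17.5, +5.4 |
| 10%/10% | -23.8, +10.1 | -20.5, +8.3 |
| 5%/20% | -31.8, +0.2 | -30.0, -4.2 |

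The source of the label matters. But the label without EUS (r = 0) is further from the truth than the label with EUS (r = 1) in 6 of the 8 cases.

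**The case against.** **The label is already settled at screening.** The aims speak of a known history of ARP or CP, entry requires a confirmed diagnosis, chart review checks it, and consent precedes study procedures. No section provides for relabelling after the study EUS or surgery. Procedures and Imaging also has MRCP and CT read blind to EUS and SWE, and foresees collecting imaging results from the chart. This largely stands. A reader might infer that the study EUS itself decides who is CP, or that Aim 1 as a whole is circular. The documents do not support that. What remains is narrower: earlier EUS evidence is not barred, its share is unknown, and no sentence says that the screening label is the one analysed. The definition also says that atrophy, irregular contour, lobular architecture and cavities alone are not diagnostic, so those findings are less exposed, though not unaffected.

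**Removing EUS from the label would cure the problem.** The calculation does not bear this out. A label without EUS counts CP missed by other imaging as ARP and can move the contrast further from the truth.

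**McNemar could be read into the chi-square tests.** On a generous reading it could, but Aim 1.2 would still have no reference standard and no definition of CP stages.

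**It is a pilot.** True, and the lack of a power calculation is not criticised here. Pilot status does not explain a directional hypothesis without a matching analysis, or a promised analysis that is absent.

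**Conclusion.** Two parts hold on the text alone. The Aim 1.2 analysis cannot test the hypothesis that EUS is more sensitive, because association tests do not distinguish which modality detects more and no reference standard is named. The assumed counts only illustrate this; the symmetry holds for any counts. The promised grayscale EUS versus histology analysis is also absent from the statistical section.

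The label point is secondary. CP-versus-ARP comparisons on calculi, side branches, calcifications and persistent duct changes may be partly circular. Neither the size nor the direction of the net bias can be known from the documents: on the assumptions shown, it runs from 32 points too low to 23 points too high, depending on r and the error rates. That supports recording where the label came from. It does not support replacing the INSPIRE label.

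This should be fixed before analysis. The descriptive catalogue of EUS findings remains worthwhile as planned.

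**What to change.** 1. **Aim 1.2.** Compare modalities only in children who have both tests, paired by child, with the rule for a positive result fixed beforehand. Report the positive count for each modality, the discordant counts in each direction, the paired difference in detection rate with its 95% CI, and exact McNemar, alongside agreement. Call the result a difference in detection rate, since extra positives may be false ones. Keep the word sensitivity for the comparison with histology, and reword the hypothesis to match.
2. **Histology.** Add grayscale EUS (Rosemont and conventional criteria, positive rule fixed beforehand) against histologic fibrosis in the roughly 20 resected children, with exact 95% CIs. Give specificity only if some children are histology-negative. State that histology is a small core, in resected patients only.
3. **Label, for the Aim 1 comparisons only.** Use the INSPIRE label confirmed at screening. Record the modality and date that established CP. Report how many CP labels rest on EUS alone, and how many children would change label after the study EUS or histology. Leave the INSPIRE reference for SWE in Aim 2 unchanged. A label without EUS is an optional extra analysis, and must carry the warning that it can move the contrast further from the truth.

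**Cost.** Analysis wording and two data fields, with no added patients or procedures. The downsides are a smaller Aim 1.2 sample and wide intervals.

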**SPECIFIC AIMS**

The aims of the proposed study are as follows:

**Aim 1: Characterize endoscopic ultrasound (EUS) findings of pediatric acute recurrent pancreatitis (ARP) and chronic pancreatitis (CP).**

Adult criteria for EUS diagnosis of CP exist, but no such criteria exist for children. As such, the applicability of current diagnostic criteria to pediatric patients is unknown.

**1.1: Catalogue grayscale EUS findings of ARP and CP in a pediatric cohort and compare to healthy controls. Hypothesis:** EUS findings of ARP and CP in pediatric patients will differ from those of adult ARP and CP and will be characteristically different

from healthy controls. *Exp1:* We will catalogue grayscale EUS findings in 40 pediatric patients with known history of ARP or CP undergoing clinically indicated EUS and will compare those with findings in 20 patients without a history of pancreatitis who are undergoing EUS for other indications.

**1.2: Benchmark grayscale EUS against other imaging modalities for diagnosis of CP, particularly early CP, in children.** *Hypothesis:* Grayscale EUS findings will be more sensitive than other imaging modalities in all stages of CP. *Exp2:* We will test associations, in blinded fashion, of grayscale EUS findings catalogued under S.A1.1 in enrolled children with findings on alternative pancreas imaging modalities performed for clinical indications. Specifically, we will correlate to endoscopic retrograde cholangiopancreatography (ERCP), magnetic resonance cholangiopancreatography (MRCP) and computed tomography (CT) performed for clinical indications within +/- 3 months of the EUS.

**Aim 2: Define the diagnostic performance of ultrasound elastography for CP and pancreatic stiffness as a measure of fibrosis in pediatric patients.**

**2.1: Define the diagnostic performance of EUS and TUS elastography for pediatric CP.** *Hypothesis:* EUS and TUS elastography will have high specificity for CP with increased stiffness in patients compared to controls. *Exp 1:* Patients enrolled under Aim 1 will undergo shear wave elastography (SWE) measurement of the pancreas during EUS. These same patients will undergo research TUS with SWE of the pancreas. SWE results by both EUS and TUS will be evaluated for diagnostic performance for CP.

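### Aim 1.2 lets the image that gave a child the CP label also be scored as a test under comparison, so sensitivity favours whichever modality supplied the label

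*Combined protocol and SAP*

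**What the plan says.** The pancreatitis cohort requires "Confirmed diagnosis of ARP or CP by INSPIRE criteria" (Study Population, Pancreatitis Cohort). Subject Recruitment puts this check at screening of patients who present for EUS: "Potential participants for the pancreatitis cohort will be reviewed to confirm diagnosis of ARP or CP by INSPIRE criteria". The label therefore normally precedes the study EUS, although the plan does not say that it is fixed at that point.

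Under Definitions, CP needs one irreversible structural change, which can be shown in three ways:
- "Ductal calculi, dilated side branches, parenchymal calcifications found in any imaging", followed by a list naming abdominal ultrasound, MRI/MRCP, CT, ERCP and EUS;
- "Ductal obstruction or stricture/dilatation/irregularities that are persistent (for >2 months) on any imaging";
- "Surgical or pancreatic biopsy specimen demonstrating histopathologic features compatible with CP".

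The Aim 1.2 hypothesis is "Grayscale EUS findings will be more sensitive than other imaging modalities in all stages of CP". The comparators are ERCP, MRCP and "computed tomography (CT) performed for clinical indications within +/- 3 months of the EUS". Under Procedures and Imaging, MRCP and CT are reviewed without knowledge of the EUS and elastography results, and ERCP images are given a Cambridge score. The Statistical analysis section plans Fisher's exact or Chi-square tests for Aim 1. It names INSPIRE as the reference for elastography in Aim 2 and names no reference for Aim 1.2.

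**The concern.** A sensitivity comparison needs a reference that neither test helped to create. Here the same MRCP can first make the diagnosis of CP and then be scored as the test whose sensitivity for CP is compared with that of EUS. In such a child, if the re-read finds the same change, the MRCP is positive and EUS can at best equal it. Because EUS findings also qualify, the reverse can happen: a child labelled on an EUS favours EUS. This is incorporation bias, and blinding the MRCP and CT readers to EUS does not remove it.

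At stake is how the hypothesis of greater EUS sensitivity is judged, particularly for early CP. The Study Design section offers these data as preliminary evidence for pediatric EUS criteria, so a distorted benchmark would carry forward into later work.

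**Working it through.** The plan gives no sensitivity, overlap or power figure to reproduce. The check therefore has two parts: what the text allows, and what that would do under stated assumptions.

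**What the text allows.** The qualifying image may be an MRCP, CT or ERCP (Definitions). The comparator is a clinical MRCP, CT or ERCP up to 3 months either side of the EUS (Aim 1.2). No section removes the qualifying image from the comparator set, asks for it to be recorded, or blinds the readers to the diagnosis or the original clinical report. The cohort has 40 children with ARP or CP (Study Procedures), and the split is not given.

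**Assumed quantities** (none is in the documents):
- f: share of CP children whose label rests on the scored comparator
- r: chance that the study re-read of that image is again positive
- g: share whose label rests on an EUS that is credited to EUS as positive
- s_C, s_E: sensitivities of comparator and EUS in the remaining children, with the two tests independent given CP

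**Formulas**
- Apparent comparator sensitivity = f·r + (1 − f)·s_C
- Apparent EUS sensitivity = g + (1 − g)·s_E
- Overlap at which a true EUS advantage vanishes (g = 0): f = (s_E − s_C)/(r − s_C)

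**1. No true difference, comparator supplies the label** (s_C = s_E = 0.70, g = 0; EUS stays at 70%)

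| f | MRCP, r = 1 | MRCP, r = 0.9 |
|---|---|---|
| 0.25 | 0.25 + 0.75×0.70 = 77.5% | 0.225 + 0.525 = 75% |
| 0.50 | 0.50 + 0.50×0.70 = 85% | 0.45 + 0.35 = 80% |
| 0.75 | 0.75 + 0.25×0.70 = 92.5% | 0.675 + 0.175 = 85% |

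EUS looks 7.5 to 22.5 points worse with a perfect re-read, and 5 to 15 points worse at r = 0.9.

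**2. A true EUS advantage** (g = 0)
- EUS 80%, MRCP 70%, r = 1: at f = 0.25 the comparison is 80% against 77.5%, so EUS still leads; at f = 0.50 it is 80% against 85%. Break-even f = 0.10/0.30 = 0.33.
- EUS 85%, MRCP 65%: break-even f = 0.20/0.35 = 0.57 at r = 1 and 0.20/0.25 = 0.80 at r = 0.9. At r = 0.8 it is 0.20/0.15 = 1.33, above 1, so EUS is never overtaken.

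**3. EUS supplies the label**
- Both at 70%, f = 0, g = 0.50: apparent EUS sensitivity is 0.50 + 0.50×0.70 = 85% against 70%, a spurious 15-point advantage.
- Mixed case, 85% against 65%, g = 0.50, f = 0.25, r = 1: EUS 0.50 + 0.50×0.85 = 92.5%, comparator 0.25 + 0.75×0.65 = 73.75%. The gap is 18.75 points against a true 20, so the two biases nearly cancel.

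**4. The extreme subset** (f = 1, r = 1). Take 20 such children with 16 EUS-positive. The EUS-positive/comparator-negative cell is empty and all 4 discordant pairs go against EUS (exact McNemar p = 0.125). The planned Fisher test has an empty column and returns p = 1, so it carries no information on which test is more sensitive.

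**The case against.** The strongest reply has four parts.

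- **Direction.** A reader might infer that children enter as CP because MRCP, CT or ERCP already showed it, so that EUS is bound to lose. The documents do not support this. EUS, abdominal ultrasound and histology also qualify, and nothing says that most labels come from the three comparators. This stands: the direction is open.
- **Re-reading.** The comparator is re-read against Table 1 or the Cambridge criteria, which are not the qualifying rules, so a positive result is not guaranteed. This also stands. It weakens the effect but does not remove it: bias remains whenever qualifying images are re-read as positive more often than that modality's ordinary sensitivity.
- **Extent.** Only qualifying images inside the window count, and only against the modality that supplied the label. Images taken after the EUS normally cannot have qualified the child, and the route through persistent ductal change normally needs more than one image. This limits f but leaves it unknown.
- **Planned output.** Aim 1 has only association tests, so no sensitivity estimate is formally planned. That is correct, but the hypothesis is stated in terms of sensitivity and will have to be judged on it.

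A reader might also infer that a child whose CP shows only on the study EUS is entered as ARP and lost. The plan does not say so. It does not state whether the study EUS can change the label, ARP has its own entry definition, and Aim 1.2 covers all enrolled children.

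**Conclusion.** The concern holds in a limited form. The image that supplies the CP label can also be scored as one of the tests in Aim 1.2, and nothing in the plan prevents it. The modality that supplied the label is favoured in those children. Where that is the comparator and the re-read reproduces the finding, EUS can only tie or lose against that modality; where it is an EUS, the bias runs the other way.

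The net direction and size cannot be calculated from the documents. The distortions shown, 5 to 22.5 points against EUS with no true difference, rest on the assumed 70% sensitivities, independence, no EUS-supplied labels, and overlaps of 25% to 75%. It would be too strong to say that the hypothesis cannot be supported: with EUS at 80%, MRCP at 70% and 25% overlap, EUS still leads by 2.5 points. Pilot status explains the absence of a power calculation, but it does not remove this bias. The change is worth making because it is cheap and the information is most reliably captured during enrolment.

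**What to change.** 1. At the chart review already planned, record the modality and date of every image or specimen that supports the CP label, including any EUS.
2. Name INSPIRE status as the reference for Aim 1.2.
3. Add an analysis rule that treats both tests alike, for example: *Each EUS-versus-modality sensitivity comparison uses the CP participants whose label is supported by evidence other than the two tests compared: a third modality, a scan outside the window that is not the scored image, or histology. Participants whose label rests only on the scored comparator, or only on EUS, are left out of that comparison and shown as separate strata.* Leaving out only the comparator-labelled children would tilt the result toward EUS.
4. Report the EUS-positive/comparator-negative and EUS-negative/comparator-positive counts in all enrolled ARP and CP children, so that possible early CP seen only on EUS stays visible. These counts are descriptive, since without independent evidence they cannot separate early disease from false positives.

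The cost is one field in the chart review and one analysis rule. The downside is smaller denominators and wider intervals for each modality, in a CP group that is only part of 40. Some dependence also remains where the supporting evidence is another scan of the same modality, so the type of supporting evidence should be tabulated.
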